Sample size estimates were calculated for our main outcome variables in Specific Aim 1 based on previously published data in normotensive and pre-hypertensive adults utilizing arterial infusions of the ET-1 receptor antagonist. A three level 2x2 General Linear Mixed Model will be used to compare normotensive and hypertensive PMW on the outcomes. The hierarchical structure is needed as sites are nested within measurements, which are nested within individuals. The model assumptions of linearity and normality, will be evaluated using Box-Cox and Shapiro-Wilk tests, respectively. Outliers and influential cases will be screened for and removed. The covariance structure will be chosen using nested model comparisons. Violations of the assumptions will be remedied using transformations suggested by the Box-Cox test. *Post-hoc* comparisons will have the Bonferroni adjustment applied. The alpha is set at 0.05 for each analysis, and will be adjusted by the number of primary dependent variables to control for multiple comparisons. In order to find a large effect ($\rho\eta^2 = 0.50$), a sample of size of 38 women is required to achieve a power greater than 0.8. In order to account for screen failures, subject attrition and potential microdialysis fiber failure, we will recruit 60 women (30 normotensive and 30 hypertensive).

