A Mixed Design ANOVA will be used to evaluate if losartan administration alters endothelial ET-1 protein expression ETB receptor expression on endothelial cells, along with ETA and ETB receptor expression on vascular smooth muscle cells in hypertensive PMW compared to that of normotensive PMW. Since values are expressed as ratios, if the assumptions of the Mixed Design ANOVA are not satisfied a Generalized Linear Mixed Model will be used. In order to find a moderately small effect ($\rho\eta^2 = .09$), a sample of size of 38 is required to achieve a power greater than 0.8. The model also assumes of linearity, sphericity, and normality, which will be evaluated using Box-Cox, Mauchly's, and Shapiro-Wilk tests, respectively. Outliers and influential cases will be screened for and removed. *Post-hoc* comparisons will have the Bonferroni adjustment applied. The alpha is set at 0.05 for each analysis, and will be adjusted by the number of primary dependent variables to control for multiple comparisons. Although we are planning on matching our groups based on age, body composition, VO_2max , and time since menopause, these may be potential covariates will be compared between groups using t-tests for continuous data and tests for χ^2 tests for categorical data. If a covariate is significantly different between groups it will be included in the analysis.

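### The 38 women called required for Specific Aim 1 do not follow from the stated effect of 0.50, and the basis of the same 38 for an effect of 0.09 is not stated

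*Combined protocol and SAP*

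**What the plan says.** The sample-size text is in the two paragraphs under the heading Statistical Plan, at the end of the combined document.

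**First paragraph (Specific Aim 1, main outcomes).** The analysis is given as "A three level 2x2 General Linear Mixed Model will be used to compare normotensive and hypertensive PMW on the outcomes". On the significance level: "The alpha is set at 0.05 for each analysis, and will be adjusted by the number of primary dependent variables". The number of those variables is not given. The effect is called large and printed as ρη² = 0.50, and for it "a sample of size of 38 women is required to achieve a power greater than 0.8". The allowance for losses comes after that figure: "In order to account for screen failures, subject attrition and potential microdialysis fiber failure, we will recruit 60 women", 30 in each group.

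**Second paragraph (protein and receptor expression).** Here "A Mixed Design ANOVA will be used to evaluate if losartan administration alters endothelial ET-1 protein expression" and receptor expression in hypertensive compared with normotensive women. The effect is called moderately small and printed as ρη² = .09. The sample size is the same: "a sample of size of 38 is required to achieve a power greater than 0.8". The alpha rule is repeated.

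Neither paragraph names the model term behind the power figure, the correlation between visits, or the effect-size convention beyond the printed symbol.

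**The concern.** Partial eta-squared of 0.50 is a very large effect: f² = 0.50/(1 − 0.50) = 1, which for two equal groups is a difference of two standard deviations. A study needs few participants to detect that, so 38 as a minimum looks too high. The same 38 is then given for 0.09, where f² = 0.09/0.91 = 0.099, about one tenth as large.

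The 38 matters because it is the only completer target in the plan, and recruitment of 60 is built on it. If it does not belong to 0.50, the first paragraph does not tell the reader what 38 completers can detect on the main outcomes, or how much a shortfall in completers would cost.

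**Working it through.** **Inputs from the plan:** effect 0.50 (first paragraph) and 0.09 (second paragraph), power above 0.8, base alpha 0.05, equal groups, and a 2x2 model, so that each main effect and the interaction has 1 df.

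**Assumptions:** the printed symbol means partial eta-squared of the tested term. Alpha is divided by 1, 2, 4 or 8, for illustration. N rises in steps of 2.

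**Formula.** Noncentral F with df 1 and N − 2, and f² = η²/(1 − η²). The noncentrality is λ = f²N or, on the stricter convention, λ = f²(N − 2). Ranges below cover both.

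**1. Attempt to reproduce 38 at 0.50 (f² = 1).** At alpha 0.05, N = 10 gives λ = 10 or 8 and power 0.79 or 0.70. N = 12 gives λ = 12 or 10 and power 0.88 or 0.81. So 12 is the required N.

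| Alpha | Required N | Power at N = 38 |
|---|---|---|
| 0.05 | 12 | above 0.99 |
| 0.025 | 14 | above 0.99 |
| 0.0125 | 16-18 | above 0.99 |
| 0.05/8 = 0.00625 | 18-20 | above 0.99 |

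At alpha 0.001, equivalent to 50 primary variables, 24-26 women suffice. Alpha would have to fall to roughly 0.00001 to 0.00002 before 38 became the required N. The loss allowance cannot explain the gap, because it is applied after 38: (60 − 38)/60 = 36.7%.

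**2. The 0.09 statement, tested-term meaning (f² = 0.099).** At alpha 0.05 and N = 38, power is 0.45-0.47, and 82-84 women are needed. This holds for a group term or a group-by-visit term tested against its own error, because partial eta-squared of the tested term already absorbs the visit correlation.

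**3. The 0.09 statement, scaled to single-visit variance.** For a two-visit interaction, λ = 2f²N/(1 − ρ), where ρ is the correlation between visits. With N = 38 and alpha 0.05, power is 0.76 at ρ = 0, 0.80 at ρ = 0.1 and 0.97 at ρ = 0.5. Power passes 0.8 only if ρ is at least about:

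| Alpha | Smallest ρ for power above 0.8 at N = 38 |
|---|---|
| 0.05 | 0.09 |
| 0.025 | 0.26 |
| 0.0125 | 0.38 |
| 0.00625 | 0.47 |

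On this scale 0.09 is a different quantity. The tested-term partial eta-squared is x/(1 + x) with x = 2f²/(1 − ρ). That gives about 0.17, 0.18 and 0.28 at ρ = 0, 0.1 and 0.5.

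**4. What 38 completers detect at 80% power (tested-term partial eta-squared).** 0.18-0.19 at alpha 0.05, 0.21-0.22 at 0.025, and 0.24-0.25 at 0.0125.

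**The case against.** The best defence is that nothing is lost. Power at 38 does exceed 0.8 for an effect of 0.50, and the discrepancy is conservative. An ordinary explanation is available: one sample size was set for the whole study by the smaller effect and then repeated for Specific Aim 1. The two paragraphs may also concern different terms, a group comparison in the first and a losartan-related change in the second. All of this stands as a possibility. The plan does not say it, however. The first paragraph presents its estimate as calculated for the Specific Aim 1 outcomes and ties 38 to 0.50.

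A second defence is that more complex tests need more women. With 7 numerator df at alpha 0.00625, the required N is 32 or 38, depending on the convention. But each term of a 2x2 model has 1 df.

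Third, the words partial eta-squared never appear. The plan prints only a symbol, so this is the natural reading rather than a stated fact.

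A reader might infer that the two paragraphs contradict each other. They would do so only if they used the same term, metric and alpha, and the text does not establish that. A reader might also infer that 0.50 was really Cohen's f (partial eta-squared 0.20). In that case power at 38 for a plain group test would be 0.83-0.85 at alpha 0.05 but 0.74-0.77 at 0.025. Nothing in the documents supports that relabelling over any other.

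**Conclusion.** The point holds as a reporting error. At 0.50, read as partial eta-squared, the stated model needs about 12 to 20 women over the alpha divisors 1 to 8, not 38. The range depends on those assumed divisors, but the conclusion does not: 50 primary variables would still need only 24-26. Either the effect size, its metric, or the claim that 38 is needed must be wrong.

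The documents do not support the stronger conclusion that the trial is underpowered for its stated main effect, or that 38 or 60 should change. Nor is the 0.09 statement shown to be wrong. It fails under the tested-term meaning (82-84 needed at alpha 0.05). It holds if 0.09 is scaled to single-visit variance and the visit correlation is about 0.1 or more at alpha 0.05, with higher correlations needed at adjusted alphas. The plan gives neither the convention nor the correlation, so its basis cannot be judged until they are stated.

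**What to change.** Keep 38 completers and 60 recruited.

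- **First paragraph:** correct or relabel the 0.50, or say that another analysis set 38. State the effect that 38 completers detect at 80% power at the adjusted alpha. As tested-term partial eta-squared this is about 0.18-0.19 / 0.21-0.22 / 0.24-0.25 at alpha 0.05 / 0.025 / 0.0125.
- **Second paragraph:** restate power at 38, giving the tested term, effect-size convention, visit correlation and alpha divisor.
- **Both:** state the number of primary dependent variables. Label any interaction effect that is scaled to single-visit variance as such, because those values are smaller than tested-term values and are easily mistaken for them.

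The cost is a change of wording in the Statistical Plan, with no added participants or visits. The downside is that the restated figures may look less favourable than the present ones.

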Hypertension is major health problem for postmenopausal women. Hypertension is more likely to be uncontrolled in women, despite medication use. Medications to block the angiotensin II pathway are commonly used to treat hypertension. However, recent data in animals suggest that multiple pathways are involved in blood pressure control in females. Specifically, blocking the angiotensin II pathway along with the endothelin-1 pathway resulted in a larger drop in blood pressure in these animals compared to single drug therapy. These blood pressure lowering effects observed in the female animals may be related to the interactions between angiotensin II and endothelin-1. Both angiotensin II and endothelin-1 are potent vasoconstrictors that can cause an increase in blood pressure, and these substances interact to cause additive effects on constricting blood vessels. The aims of this study are to examine how angiotensin II and endothelin-1 interact to regulate blood vessel function in hypertensive postmenopausal women. To do this, we will recruit women with elevated blood pressure not taking blood pressure medications, and test their blood vessel function on 2 separate visits: 1) baseline, and 2) after 14-days of losartan (an angiotensin II receptor blocker). Blood vessel function will be assessed using a technique called microdialysis, which involves placing tiny sterile plastic tubes (microdialysis probes) in the surface layer of the skin on the forearm, and blood flow will be measured using a small disk with a laser. We will also recruit normotensive women to complete 2 visits to assess blood vessel function pre/post 14 days as a control (no losartan administration).

6. PROCEDURES Describe all procedures involving human subjects for this protocol. Include copies of all surveys and research measures.

We will recruit postmenopausal women with high BP (≥ 130 and/or 80 mmHg) and normotensive postmenopausal women (ages 50-70 years). Women with high BP will complete 5 visits (screening/orientation, VO₂max test, Blood Vessel Assessment 1, Blood draw to check electrolytes and kidney function, and Blood Vessel Assessment 2), and normotensive women will complete 4 visits (screening/orientation, VO₂max test, Blood Vessel Assessment 1, and Blood Vessel Assessment 2).

Procedures in Women with high BP (5 visits):

Visit 1: Screening/orientation: The first visit is about 1 hour long and includes

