Perfusion of the ET-A and ET-B receptor antagonists, BQ-123 and BQ-788, either in arteries or skin vessels in humans, is an acceptable and safe experimental technique. Included is a list of the published research studies utilizing this technique:

- ¹Wenner MM et al. Endothelin B receptor contribution to peripheral microvascular function in women with polycystic ovary syndrome. JPHYS 2011.
- Kellogg DL et al. Gender differences in the endothelin-B receptor contribution to basal cutaneous vascular tone in humans. J Appl Phys 2001.
- Stauffer BL et al. Sex differences in endothelin-1-mediated vasoconstrictor tone in middle-aged and older adults. Am J Physiol Regul Integr Comp Physiol. 2010.

Losartan administration: At the completion of visit 3, women with high BP will be given 7 days of losartan (50mg), and be instructed to take the study medication once per day (at nighttime before bed). Losartan is a medication given to treat hypertension. Losartan administration will be overseen by [name].

Visit 3: Blood draw. This visit will occur one week after starting losartan. This visit will last \sim 20 minutes. Participants will report to the Physiology Core Laboratory at the STAR Health Sciences complex. Participants will be seated, and 10mL of blood will be drawn from a vein. Serum electrolytes and creatinine will be assessed to ensure using losartan in not having adverse effects on kidney function or electrolytes. If serum potassium is >5.2 mmol/L or creatinine is $>50\%$ over baseline values, the PI will contact the study physician [name], and he will determine if the medication will be discontinued and the participant be removed from the study. Elevated levels

typically resolve on their own upon cessation of drug therapy. Rarely, acute renal injury or cardiac arrhythmia's may develop. Additional medical follow-up may be instructed by [name], determined on a case-by-case basis (depending on individual responses to the medication), either to the emergency room or to the PCP. They will also be weighed. Women will be given another 7 days of losartan (50mg) and instructed to take the medication once per day (at nighttime before bed). Women will also be given a 24 hour ambulatory blood pressure monitor, and instruction on how to wear and operate the monitor. They will don the monitor the day before Visit 4. The blood pressure monitor measures BP every 20 minutes during the day, and every 30 minutes at night. Women will return the monitor the fourth visit.

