7. STUDY POPULATION AND RECRUITMENT

Describe who and how many subjects will be invited to participate. Include age, gender and other pertinent information.

Normotensive and postmenopausal women and women with high BP (ages 50-70 years) will be recruited. A total of 60 women will be recruited (30 normotensive and 30 high BP). Subjects will be recruited from campus and local community- posting flyers and advertisement in local newspapers, in physicians' offices, community centers or events, through professional societies, or online (UD classifieds, website). In addition, we will conduct blood pressure screenings in the community.

Attach all recruitment fliers, letters, or other recruitment materials to be used. If verbal recruitment will be used, please attach a script.

Recruitment flyers are attached.

Describe what exclusionary criteria, if any will be applied.

Women will be excluded from the study if they have a history of any heart disease, kidney or liver disease, history of blood clots, pulmonary embolism, deep vein thrombosis, stroke, cancer, diabetes, or any other chronic disease. Women will also be excluded from the study if they use tobacco products (including cigarettes and chewing tobacco), are using hormone therapy, are pregnant, or if their body mass index is greater than 35. Women will be excluded if resting blood pressure is greater than 180/100 mmHg, or less than 100/60 mmHg at the initial screening.

Describe what (if any) conditions will result in PI termination of subject participation.

We are assessing serum electrolytes, creatinine and blood pressure at baseline and after 1 week of losartan administration. If serum electrolytes (potassium >5.2 mmol/L), creatinine levels (>50% over baseline values) rise too high, or blood pressure (less than 100/60 mmHg) drops too low, the study physician [name] will be contacted to determine if the subject will be instructed to stop taking the medication and will be excluded from the study.

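### Aim 2 lists a sphericity check that is empty with two visits, and no check of equal change variance between groups, which its group-by-visit test assumes

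*Combined protocol and SAP*

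**What the plan says.** Statistical Plan, second paragraph: "A Mixed Design ANOVA will be used to evaluate if losartan administration alters endothelial ET-1 protein expression", together with receptor expression, in hypertensive compared with normotensive women. On assumptions it says "The model also assumes of linearity, sphericity, and normality", "which will be evaluated using Box-Cox, Mauchly's, and Shapiro-Wilk tests, respectively". Equal variance between groups appears in neither paragraph of the Statistical Plan, and no test for it is listed. If the ANOVA assumptions are not met, a Generalized Linear Mixed Model (GLMM) replaces it, with no variance structure stated.

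The opening summary sets two measurement occasions for the women with high blood pressure: "test their blood vessel function on 2 separate visits: 1) baseline, and 2) after 14-days of losartan". The normotensive women are studied "pre/post 14 days as a control (no losartan administration"). Under section 6 (Procedures), endothelial cells are collected at Blood Vessel Assessments 1 and 2. The one-week visit in the high-BP group is for safety: "Participants will be seated, and 10mL of blood will be drawn from a vein", for electrolytes and creatinine. It adds no third expression measurement.

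Under section 7, on termination of participation, abnormal potassium, creatinine or low blood pressure after one week of losartan leads to contact with the study physician, who determines whether the woman "will be instructed to stop taking the medication and will be excluded from the study".

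**The concern.** The named variance check cannot detect anything, and the variance assumption that could fail is not on the list. With two groups and two visits, the interaction F is the square of a pooled-variance t statistic on each woman's change. It is valid when change has the same variance in both groups, or nearly so when the groups are of equal size. Two features of the design bear on this separately:

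- **Variance.** Only one group is treated, so variation in response to losartan may add to measurement noise in that group alone.
- **Group size.** The losartan removal rule applies to that group alone, so its number of completers may fall below the other group's.

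If the smaller group has the larger variance, the pooled test rejects too often. If it has the smaller variance, the test rejects too rarely. At stake is whether the Aim 2 losartan comparison runs at its stated alpha.

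**Working it through.** **Inputs from the documents.** Two groups; two occasions; 30 women recruited per group; alpha .05, to be divided by a number of primary outcomes that is not stated. Four expression measures are listed, so .05/4 = .0125 is used as a second level. **Assumed, because the documents give neither:** completer numbers, and the ratio of change SDs (losartan to control).

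**The plan's own figure.** The Aim 2 sample size is 38 for partial eta squared .09, so f² = .09/.91 = .0989. It cannot be reproduced uniquely, because the within-woman correlation is not given. For group-by-visit at alpha .05 the required N is 42, 30 and 22 at correlations 0, .3 and .5, and 38 at about .1. Nothing below depends on this figure.

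**Step 1: sphericity.** For k within-woman levels, Mauchly's test has k(k−1)/2 − 1 degrees of freedom. With k = 2 this is 2·1/2 − 1 = 0. There is one difference score, W = 1 always, and the test cannot reject.

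**Step 2: the test that is run.** Let d1 and d0 be the mean changes, s1 and s0 the SDs of change, and n1 and n0 the completers (losartan, control).

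- Pooled: t = (d1 − d0) / √[sp²(1/n1 + 1/n0)], with sp² = [(n1−1)s1² + (n0−1)s0²] / (n1+n0−2). The interaction F equals t².
- Welch: t = (d1 − d0) / √(s1²/n1 + s0²/n0), with Satterthwaite df.

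**Step 3: type I error of the pooled test at nominal .05** (simulation under no mean difference in change).

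| Losartan / control completers | SD ratio 1.5 | SD ratio 2 | SD ratio 0.5 |
|---|---|---|---|
| 30/30 | .051 | .052 | .052 |
| 28/30 | .054 | .057 | .047 |
| 27/30 | .055 | .059 | .045 |
| 25/30 | .059 | .065 | .040 |
| 19/24 | .062 | .070 | .038 |
| 19/28 | .069 | .083 | .030 |
| 19/30 | .073 | .090 | .026 |

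At nominal .0125 and 19/30, SD ratios 1.5 and 2 give about .022 and .031. Welch stays at about .05 in every row, and at about .013 for nominal .0125.

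**Step 4: power cost when variances are equal.** At 19/28 with a true difference of 0.9 SD, power is .842 pooled and .839 Welch: .842 − .839 = .003, or 0.3 points.

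**The case against.** The strongest reply is that the plan recruits 30 and 30, and at equal numbers the pooled test is sound. The 19/30 row needs 11 of 30 losartan women lost (37%) and no control lost, whereas the plan expects screen failures, attrition and fibre failure without confining them to one group. Removal under the safety rule is at the physician's discretion, and no rate is given. This stands, and it is why the near-planned rows matter most.

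The variance ratios are also demanding. If response is independent of noise, SD ratios of 1.5 and 2 need individual responses with SD √(1.5² − 1) = 1.12 and √(2² − 1) = 1.73 times the control change SD, yet averaging zero under the null tested. Nothing in the documents points to a pattern that strong. This stands too.

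A reader might infer four stronger things that the documents do not support:

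- **That the losartan result will be declared significant too often.** Excess rejection needs a smaller and more variable losartan group. A smaller and less variable group gives the reverse.
- **That safety withdrawals make the variances unequal.** They change group size. Removing strong reactors, or the planned removal of outliers, could narrow the spread.
- **That the GLMM fallback excludes this assumption.** Its trigger is worded for the ANOVA assumptions in general. The gap is that no listed diagnostic would show this failure, and no group-specific variance is stated if the GLMM is used.
- **That the Mauchly step distorts a result.** A check that cannot reject changes nothing.

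Mauchly's test would have content if a within-woman factor with three or more levels were intended, but the plan treats the markers as separate dependent variables.

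**Conclusion.** The point holds as a minor one. Two facts follow from the text: the sphericity check is empty with two visits, and equal change variance between groups is neither named nor checked, although only one group is treated. The size is conditional on assumed completer numbers and SD ratios. At planned or near-planned numbers the error is at most about one percentage point of alpha. It reaches .06 to .09 only with a markedly smaller and more variable losartan group (19/24 to 19/30), and the test becomes conservative (.03 to .04 over the same numbers) if that group has half the control SD. The case for acting is that the remedy holds its level in all these settings at almost no cost, not that inflation has been shown.

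**What to change.** In the second paragraph of the Statistical Plan, prespecify that group-by-visit is tested with unequal variances from the outset, with no preliminary variance test deciding the method:

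- Without covariates: a Welch test on change.
- With covariates, which the plan allows: a heteroscedastic model on change, or a mixed model in which the whole covariance matrix differs by group, with Satterthwaite or Kenward-Roger df. Letting only the residual variance differ is not generally equivalent to Welch.

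If the GLMM fallback is kept, state its variance structure by group. Deleting the Mauchly step is tidying only.

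Cost: SAP wording, and about 0.3 points of power if variances are equal. It needs no extra participants, visits or data.

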Visit 4: Blood Vessel Assessment 2: The fifth visit is will occur 14 days after beginning losartan. This visit is approximately 5 hours long, and is identical to Visit 2 (Blood Vessel Assessment 1).

Visit 5: VO₂max Testing. This visit will last ~1 hour. Participants will be fasted from alcohol and caffeine for 12 hours, food for 4 hours, and exercise for 24 hours prior to testing. Exercise tests will be conducted in the stress testing laboratory in the NMPCC and overseen by a Certified Exercise Physiologist and Nurse Practitioner after clearance from the study physician, [name]. A resting 12-lead ECG and blood pressure will be taken in the supine and standing position. If resting BP is $\geq 200/110$ mmHg, the test will not be performed. A standard ramp treadmill protocol will be used, consisting of 1.5-minute stages where the speed and grade is increased incrementally. Expired gases will be collected and analyzed using the Parvo Medics Metabolic Cart. Exercise BP, HR, and ECG will be taken throughout, along with ratings of perceived exertion. This is a symptom-limited metabolic stress test; test termination criteria are based on ACSM guidelines (RER ≥ 1.10 , plateau in HR or VO₂ despite increased workload), and absolute indications for test termination such as chest pain, ECG abnormalities or arrhythmias, BP $>250/115$ mmHg, or participants request to stop. [name] will review the exercise test results. The NMPCC will send the test results to be read and interpreted by their cardiologist, [name]. In the event of a positive test or if additional follow up is needed, the NMPCC will contact the participant's primary care doctor.

Procedures in Normotensive Women (4 visits):

Visit 1: Screening/orientation: The first visit is about 1 hour long and includes

- 1). Completion of informed consent, medical history, and menstrual cycle history
- 2). Measures of height and weight,
- 3). Measures of resting blood pressure and 12-lead electrocardiogram
- 4). Blood Draw

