Visit 4: VO₂max Testing. This visit will last ~1 hour. Participants will be fasted from alcohol and caffeine for 12 hours, food for 4 hours, and exercise for 24 hours prior to testing. Exercise tests will be conducted in the stress testing laboratory in the NMPCC and overseen by a Certified Exercise Physiologist and Nurse Practitioner. A resting 12-lead ECG and blood pressure will be taken in the supine and standing position. If resting BP is $\geq 200/110$ mmHg, the test will not be performed. A standard ramp treadmill protocol will be used, consisting of 1.5-minute stages where the speed and grade is increased incrementally. Expired gases will be collected and analyzed using the Parvo Medics Metabolic Cart. Exercise BP, HR, and ECG will be taken throughout, along with ratings of perceived exertion. This is a symptom-limited metabolic stress test; test termination criteria are based on ACSM guidelines (RER ≥ 1.10 , plateau in HR or VO₂ despite increased workload), and absolute indications for test termination such as chest pain, ECG abnormalities or arrhythmias, BP $>250/115$ mmHg, or participants request to stop. The NMPCC will send the test results to be read and interpreted by their cardiologist, [name]. In the event of a positive test or if additional follow up is needed, the NMPCC will contact the participant's primary care doctor.

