9. COMPENSATION

Will participants be compensated for participation?

Yes

If so, please include details.

Women with high BP: Subjects completing all aspects of the study will receive \$275.00. If a participant is excluded due to elevated blood levels (visit 3), they will receive \$100.00. Participants that do not complete visit 5 (exercise test) will receive \$225.00. They will receive the compensation at the end of the study in the form of a check.

Normotensive women – hormone intervention: Subjects completing all aspects of the study will receive \$200.00. They will receive the compensation at the end of the study in the form of a check. Participants that do not complete visit 4 (exercise test) will receive \$150.00.

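### Covariates enter the non-randomised group comparison only when a weak significance test flags them, and the protocol disagrees on when one of them, VO₂max, is measured

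*Combined protocol and SAP*

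**What the plan says.** **Covariate rule.** The second paragraph of the Statistical Plan (mixed-design ANOVA for protein and receptor expression) has a sentence beginning "Although we are planning on matching our groups based on age, body composition", which goes on to VO₂max and time since menopause. These are compared between groups by t-tests or χ² tests. Then: "If a covariate is significantly different between groups it will be included in the analysis". The matching has no stated ratio, caliper or procedure. The level of the balance tests is not given.

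**Aim 1 model.** The first paragraph compares the same two groups: "A three level 2x2 General Linear Mixed Model will be used to compare normotensive and hypertensive PMW on the outcomes". It states no covariate rule.

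**VO₂max timing.** The Section 6 overview says "Women with high BP will complete 5 visits (screening/orientation, VO₂max test, Blood Vessel Assessment 1", so the test comes second; the same order is given for normotensive women. The detailed procedures put it last in each group: "Visit 5: VO₂max Testing. This visit will last ~1 hour" (high BP) and "Visit 4: VO₂max Testing. This visit will last ~1 hour" (normotensive). Section 9 agrees with the detailed procedures and allows for women who skip the test: "Participants that do not complete visit 5 (exercise test".

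**The concern.** Because the groups are not randomised, a covariate difference is a confounding question, and its p-value does not answer it. What matters is the size of the imbalance and how strongly the covariate relates to the outcome. At these sample sizes a non-significant test is compatible with an imbalance large enough to matter, and under this rule such an imbalance is left uncorrected. The data also choose the model.

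The uncorrected imbalance falls on the group main effect. The group-by-time contrast, which is the stated losartan question in the second paragraph, is affected only if a covariate is related to change over the 14 days. A covariate entered as a main effect alone would not correct that.

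If VO₂max is measured last, it cannot guide matching before the assessments, and in the high-BP group it is not a baseline variable. No interval from last dose to exercise test is given, so any shift in it is unknown. In the high-BP group the test also needs the study physician's clearance, based on blood pressure and screening results (Section 6, Visit 5; Section 8, exercise test). Missing VO₂max may therefore differ by group.

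**Working it through.** **Inputs.** Calculated total 38, so 19 per group if equal; recruited 60, so 30 per group (Statistical Plan, first paragraph). Age range from Section 7: "women with high BP (ages 50-70 years) will be recruited". Assumed because the documents are silent: two-sided 0.05 for the balance tests; covariate-outcome correlation r of 0.3-0.5; imbalance d after matching of 0.1-0.7 SD.

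**The plan's own figure.** The 38 cannot be reproduced uniquely, because the within-woman correlation and the number of primary variables are not stated. For partial η² = 0.09, a 2×2 group-by-time test at alpha 0.05 reaches 80% power with 38 women once the between-visit correlation is at least about 0.09. The 38 is used below only as a sample size.

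**1. Smallest difference that triggers adjustment:** t(0.975, 2n−2) × √(2/n).
- n = 19: 0.658 SD
- n = 30: 0.517 SD

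If ages were uniform over 50-70 (assumed), the SD is 20/√12 = 5.77 years, and the thresholds are 0.658 × 5.77 = 3.80 years and 0.517 × 5.77 = 2.98 years.

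**2. Chance of missing a true 0.5 SD imbalance.** Power of the two-sample t-test is 0.323 (n = 19) and 0.478 (n = 30), so it is missed 68% and 52% of the time.

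**3. Average bias under the rule.** Simulation with one outcome per woman, no true group effect and 20,000 runs per cell. Age and time since menopause correlate 0.8 and BMI is independent (both assumed); all three have the same imbalance and all three are tested. Bias in SD:

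| n per group | r | d = 0.1 | 0.2 | 0.3 | 0.5 | 0.7 |
|---|---|---|---|---|---|---|
| 19 | 0.3 | 0.018 | 0.034 | 0.043 | 0.051 | 0.037 |
| 19 | 0.5 | 0.034 | 0.058 | 0.073 | 0.084 | 0.061 |
| 30 | 0.3 | 0.017 | 0.034 | 0.041 | 0.033 | 0.014 |
| 30 | 0.5 | 0.029 | 0.055 | 0.066 | 0.055 | 0.022 |

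With a single covariate tested, bias is 0.02-0.11 SD. With all three always entered, bias is within 0.01 SD of zero. RMSE is then 3-9% smaller than under the rule at r = 0.5 (for example 0.314 v 0.341 at n = 19, d = 0.5), between 2% smaller and unchanged at r = 0.3, and 1-4% larger at r = 0. Entering only the less relevant of age and time since menopause leaves 0.01-0.07 SD.

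**4. Given an observed, non-significant difference D.** Unadjusted bias is r × D: 0.06-0.10 SD at D = 0.2 and 0.15-0.25 SD at D = 0.5. Type I error at D = 0.5 is 6-8% (n = 19) and 8-12% (n = 30), against about 5% when adjusted.

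**5. Losartan contrast.** The shift is the correlation with change times the imbalance: 0.1 × 0.3 = 0.03 to 0.3 × 0.7 = 0.21 SD of change (both factors assumed).

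**6. VO₂max order, side by side.**

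| Place | Position implied |
|---|---|
| Section 6 overview | Second |
| High BP, Visit 5; normotensive, Visit 4; Section 9 | Last |
| Both groups: monitor worn before Visit 2 is returned at the third visit | Fits second |
| High BP: losartan handed out after visit 3, yet Visit 3 is a week into losartan | Fits second |
| High BP: Visit 4 text calls it the fifth visit | Fits second |
| Normotensive: Visit 3 text calls it the fourth visit | Fits second |

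**7. What the order changes.** Suppose fitness is the confounder, with n = 19, d = 0.5 and r = 0.5 (10,000 runs). Bias is 0.248 SD if VO₂max is omitted, 0.114 under the rule, 0.002 if always entered and unshifted, and −0.099 if always entered but shifted by +0.2 SD after losartan (assumed). Across imbalances of 0.3-0.7 and r of 0.3-0.5, omitting it leaves 0.09-0.35 SD. Entering a value shifted by 0.2-0.3 SD leaves 0.06-0.15 SD in absolute size. Neither choice is safe if the test comes after treatment.

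**The case against.** The strongest reply is that the harm is small. Read as a two-group contrast, partial η² = 0.50 is f = 1.0, about 2 SD, so a bias of 0.08 SD is about 4% of it. For 0.09, f = 0.314, about 0.63 SD, and 0.08 is about 13%. Planned matching should make gaps near the threshold rare, so the 3-4 year figures are limits of the rule rather than expected differences. Main-effect covariates do not address the group-by-time contrast. The simulation is simpler than the three-level model, and its correlations are assumed. The rule does not literally say only, and since it closes the Statistical Plan it may be meant for both models. The VO₂max conflict could be called editorial.

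Much of this stands. It keeps the point below a critical one, and it is why covariate-by-time terms are proposed for the losartan contrast. It does not rescue the rule. Matching has no stated procedure, and whatever imbalance it leaves still meets the same test. No other route to inclusion is written. The VO₂max conflict is more than editorial, because it decides whether a named matching variable is measured before or after treatment in one group.

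**Conclusion.** The concern holds, as something that should be changed rather than something that invalidates the study. The thresholds of 0.66 and 0.52 SD follow from the sample sizes and an assumed two-sided 5% test. The average bias of 0.01-0.08 SD (three covariates tested) rests on the assumed correlations and imbalances. Type I error under the rule is about 6% at most in those settings, and reached 6.9% in a wider one-covariate check (correlation 0.7, imbalance 0.65 SD). The effect on the losartan contrast is conditional on covariates predicting change. The VO₂max contradiction needs no assumption; only its numerical consequence does. Confidence is medium, because the documents give no covariate-outcome correlations and no matching procedure.

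**What to change.** 1. Delete the significance condition. Name the covariates in advance and enter them in the normotensive v hypertensive models of both paragraphs, whatever their baseline p-values: age and time since menopause (both), and the plan's body composition measure. If no such measure is collected, use BMI from the recorded height and weight and say that it is a proxy. If BMI correlates 0.8 with true body composition (assumed), fixed BMI leaves 0.02-0.13 SD at imbalances of 0.3-0.7, against 0.06-0.21 SD for BMI under the present rule.
2. Add covariate-by-time terms as a sensitivity analysis for the losartan contrast.
3. Reconcile the VO₂max order across the Section 6 overview, the detailed visits in both groups and Section 9. If it is measured before losartan, add it to the main set. If after, do not call it a baseline or enrolment-matching variable; report the group comparison with and without it as a named sensitivity analysis, stating that neither version is free of possible bias from fitness.
4. Either way, state how missing VO₂max is handled (for example multiple imputation), so that women without the test stay in the main analysis.

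**Cost.** Wording and one consistent visit order; no new data. With 38 women it uses 3 of 36 error degrees of freedom (4 with VO₂max). If no covariate predicts the outcome, RMSE is up to about 4% larger (5% with VO₂max). Four covariates that explain nothing lower power for a 0.934 SD between-group contrast from 80.0% to 79.7%; if they explain 10-30% of the variance, it rises to 83.7-91.6%. At correlation 0.3 the RMSE benefit is about nil. BMI as a proxy, or VO₂max measured after losartan, would leave some bias.
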